7.3. Evaluations During Study Intervention

Study participants in both statin and placebo groups will have a Cardiac MRI (see Section 7.2 for pregnancy testing prior to MRI exams), and blood drawn for a cardio profile, lipids, CK, ALT, AST, Total Bilirubin, glucose, TSH, Hematocrit (only if gadolinium contrast is administered for the MRI) and neurohormonal biomarkers at screening/baseline, 6 months and between 24 - 27 months. Biomarkers studied include ultrasensitive troponin I (for myocellular injury); C-reactive protein, interleukin-6, tumor necrosis factor- α (systemic inflammation); and renin and aldosterone (circulating neurohormones). Additional blood samples will be drawn on participants who consented to have blood stored for future research.

See section 5.6.1 for Modification of Study Medication related to Myalgias which may require additional labs at 1 and 3 months.

See section 5.6.2 for Modification of Study Medication related to Elevated ALT, AST and CK Labs.

Neurocognitive test battery and Quality of Life Questionnaires will be obtained. At 12 and 18 months participants will be contacted by phone to assess toxicities and medication compliance. Quality of Life Questionnaires will be completed via mail.

7.4. Evaluations at Completion of Study Intervention

All study participants will have an Cardiac MRI (see Section 7.2 for pregnancy testing prior to MRI exams) and blood drawn for a cardio profile, Lipids, CK, ALT, AST, Total Bilirubin, glucose, TSH, Hematocrit (only if gadolinium contrast is administered for the MRI procedure) and neurohormonal biomarkers noted in 7.3, between 24 – 27 months. Additional blood samples will be drawn on participants who consented to have blood stored for future research

Neurocognitive testing and Quality of Life Questionnaires will be obtained. Follow-up assessments will include laboratory evaluations, pill counts, and structured interviews assessing outcomes and potential adverse events.

7.5. Post-intervention Follow-up Period.

Patients completing 24 months of study medication will be followed for an additional 30 days after the last dose of study medication to evaluate any related adverse events. After the 25 month contact, the patient is no longer followed and data is no longer collected from the patient.

7.7. Study Parameters Table

Study agent or placebo should be started when received. The patient must receive 2 doses prior to first chemotherapy tx. and those 2 doses may be given at least 12 hours apart. If necessary, due to time constraints, patient may be given 2 tablets at the same time at least 90 minutes prior to first chemotherapy tx. All evaluations/procedures are to be completed within + or – 30 days of specified time unless indicated otherwise. **Note: 24 month MRI should be obtained within 30 days prior to the last dose of study medication.**

Evaluation Procedure	Screening (C)	Baseline (D)	1 & 3 Mths (G)	6 Mths	12 Mths	18 Mths	between 24 - 27 Mths	1 Mth Post Final Assessment	
Informed Consent	X								
Demographics (p. 6 of enrollment form)	X								
Nurse Exam		X		X			X		
Cardiac/Vascular MRI (A)(B)		X (A1)(B)		X (A2)(B)			X (A3)(B)		
Screening labs (C)	X								
CV Risk Calculator		X							
General Labs (D) (E)		X		X			X		
Biomarker Labs (F)		X		X			X		
Future Research Lab (if pt. consents)		X		X			X		
ALT/AST and CK - Above normal at baseline (G)			X						
Unscheduled ALT/AST/ CK for myalgias/ elevated levels (See Section 5.6)									
Baseline Booklet (H)		X							
6 Month Booklet (H)				X					
12 Month Booklet (H)					X				
18 Month Booklet (H)						X			
24 Month Booklet (H)							X		
Flow Sheet/Addenda		X	X	X	X	X	X		
Phone Contact Form					X	X			
MRI Encounter Form (I)		X		X			X		
Current Med Form		X		X	X	X	X		
Medication Diaries & pill count (J)		Every other month							
Chemo Form	Submit this form after each course (not cycle) of chemotherapy								
RT Form	To be completed when last RT tx. is received or indicating patient will not receive RT.								
Open Label Form	If placed on a statin by their physician. (See Appendix 12 Statin Physician Update)								
Early Withdrawal Treatment/Consent	Submit if patient withdraws from active tx, or withdraws consent prior to end of .study.								

Screening Form	Submit this form every month.	
1 Month Post Contact Form (K)	For patients completing between 24 -27 months of study med – Submit this form 30 days after last dose of study medication.	X

- A1** - Baseline MRI's are required. If a routine standard of care LVEF is obtained by ECHO or MUGA this result should be documented on the flow sheet or the enrollment form.
- A2** - 6 month MRI should be obtained between 5 and 7 ½ months once anthracycline therapy has been completed and tissue expanders (if applicable) have been removed. For time periods outside of these ranges, special permission for extenuating circumstances (e.g., significant healthcare issue warranting hospitalization) may be obtained by direct contact with [name], the study PI. If it is determined a patient cannot have a 6 month (5-7 1/2 month) MRI, the patient will continue on study as per protocol.
- A3** - 24 – 27 month MRI should be obtained within 30 days prior to the last dose of study medication. It is important to recognize that this sample point is very important for the conduct of the study. For scans that need to be performed outside of this range of time, special permission for extenuating circumstances (e.g., significant healthcare issue warranting hospitalization) may be obtained by direct contact with [name], the study PI.
- B** - It is suggested that a negative serum or urine pregnancy test be performed within 10 days of each MRI exam for all women of childbearing potential.
- C** - Screening labs must be within 30 days prior to enrollment. Screening CMP results should be used for Baseline CMP (ALT, AST, Glucose, Total Bili), Lipid Panel, Creatine Kinase, TSH -- Serum HCG must be drawn within 10 days prior to enrollment in women of child-bearing potential
- D** - Baseline evaluations must be completed prior to start of chemo.
- E** - Hematocrit - Obtain only when gadolinium contrast is administered for the Cardiac MRI.
- F** - Biomarkers (C-reactive Protein, Troponin-I, Aldosterone, Interleukin-6, TNF α , Renin)
- G** - Repeat labs at 1 and 3 months should be collected within + or - 7 days if baseline values are above normal but within eligibility limits.
- H** - Booklets for the additional cognitive and QOL questionnaires are described in Section 11.1.
- I** - Submit MRI Encounter Form on all patients. If MRI not performed, indicate this on MRI Encounter Form and submit to the Wake Forest NCORP Research Base.
- J** - For both blinded and open label patients, medication diaries should be collected in-person or by mail every other month. A pill count is required when the patient is seen at 6 months, 24 months or at any time the patient discontinues the study medication.
- K** - 1 Month Post Final Assessment contact form - Patients completing 24 - 27 months of study medication should be followed for an additional 30 days after last dose of study medication for related adverse events.

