3. SUMMARY OF STUDY PLAN

3.1. Overview of Study and Study Design

We propose a double-blind, placebo-controlled randomized clinical trial of 40 mg of atorvastatin (Lipitor®) or placebo per day in 278 men and women age \geq 21 years old scheduled to receive Anthracycline-based chemotherapy for Stage I-III including inflammatory Breast Cancer, or lymphoma Stage I-IV with a $>$ 2 year life expectancy. Innovative noninvasive MRI measures of LV volumes, EF, myocardial strain, PWV, arterial wall thickness, and other serum markers plus key patient reported outcomes including cognition and quality of life measures will be collected at baseline, 6 and 24 months after initiating treatment with Anthracycline-based therapy. In addition, participants will be contacted by telephone to assess medication compliance/toxicities and Quality of Life at 12 and 18 months. Patients completing at least 24 months but no longer than 27 months of study medication will be followed for an additional 30 days after the last dose of study medication to evaluate any study related adverse events.

3.1.1 COVID-19 - Due to the inability to obtain a final 24 month assessment (related to social distancing because of Coronavirus) of the primary outcome measures for the Prevent study, this study has been amended to provide additional study drug to remaining participants for an additional 3 months. This provision extends the window of opportunity to collect the final study outcome measures within 27 months of beginning the study at a time when social distancing is not required due to the presence of the coronavirus in our communities. This amendment allows for final study related assessments to be accomplished with participants still receiving the study drug. Our statistical analyses which is ongoing to examine the change in outcomes over time allows the exact time between baseline and follow up to be accounted for (I.e. the exact number of days between visits). This modification to allow patients to have their final measurements after 24 months (I.e. 27 months) will not negatively impact our ability to evaluate the stated hypotheses and outcomes for this study. Moreover, this change we will ensure that to the best of our ability we will evaluate the efficacy of the study drug on patients who take the drug until their final outcome assessments, as was the intention of our trial.

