5.6. Medication Modification

5.6.1 Medication Modification for Myalgias

Grade 1 Myalgias – If needed patient may take NSAIDs/analgesics at the discretion of the treating physician. Frequently this type of skeletal pain is not relieved with these medications.

Grade 2 or 3 Myalgias - Study medication should be held and patient instructed in the use of NSAIDs/analgesics per treating physician orders. ALT, AST and CK should be drawn within 24 hours.

- If labs are in acceptable range (ALT and AST are $< 3 \times \text{ULN}$ and CK $< 2.5 \times \text{ULN}$) study medication should be resumed.
- If Grade 2 or 3 myalgias redevelop, study medication should be discontinued. Patient will be considered off study medication but will continue to be followed.
- If ALT and/or AST are $> 3 \times \text{ULN}$ and/or CK $> 2.5 \times \text{ULN}$ study medication should be discontinued. Patient will be considered off study medication but will continue to be followed.

Any patient with suspected rhabdomyolysis/compartment syndrome of lower leg or rupture of tendon should stop the study medication immediately. The treating physician should assess the patient and order CK isoenzymes and/or other labs as deemed necessary. Patient will remain on study (off study medication) and be followed as usual.

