6.3 Drug Availability and Description

Atorvastatin will be manufactured and supplied by Greenstone. The study agent will be directly supplied to Biologics, Inc. who will fill pill bottles and create labeled prescriptions.

Biologics, Inc. will provide procurement, over encapsulation and placebo manufacture services.

Atorvastatin - supplied as 40mg capsules packaged in 90-count bottles. Biologics will procure the active supply from wholesaler for use in this study. The active supply will then be over encapsulated to

maintain the blind of the study. Each bottle of over encapsulated Atorvastatin will be 180-ct. Biologics anticipates making two purchases of active supply, one prior to the start of the study and one at year two, to accommodate the five year length of the trial and expirations of the product.

Prior to study launch, Biologics will procure and over encapsulate approximately 54,720 tablets. At year two, Biologics will procure and over encapsulate approximately 54,720 tablets to complete the study.

Placebo - A placebo is a substance, like a sugar pill, that is not thought to have any effect on the disease or condition. Placebos are used in research studies to see if the drug being studied really does have an effect.

Matching placebo supplied as capsules packaged in 90-count bottles. Biologics will facilitate the manufacture of a matching placebo to maintain the blind of the study. Each bottle of matching Placebo will be 180-ct. Biologics anticipates the manufacture of two batches of the matching placebo, one prior to the start of the study and one at year two, to accommodate the five year length of the trial and expirations of the product.

Prior to study launch, Biologics will facilitate the manufacture of approximately 54,720 placebo capsules. At year two, Biologics will facilitate the manufacture of approximately 54,720 placebo capsules to complete the study.

Shipment 1

12 Month Patient Specific Supply

- Biologics will ship 2 bottles of study drug to the study site
- Months 1-12: 2 bottles (180-ct)

At approximately month 11, Biologics will contact the site to prepare the subsequent shipment of study drug for the patient to complete months 13-24.

Shipment 2

12 Month Patient Specific Supply

- Biologics will ship 2 bottles of study drug to the study site
- Months 13-24: 2 bottles (180-ct)

Shipment 3 (if applicable)

12 Month Patient Specific Supply

- Biologics will ship 1 bottle (180 ct) of study drug to the patient if needed.

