At baseline, if a routine standard of care ECHO or MUGA is obtained and available at the time of enrollment, the LVEF result should be documented on the enrollment form. If the LVEF result is available after enrollment, record the result on the flow sheet. .

An MRI should be obtained between 5 and 7 ½ months. All anthracycline therapy should be completed and tissue expanders (if applicable) removed before obtaining the cardiac MRI. For time periods outside of these ranges, special permission for extenuating circumstances (e.g., significant healthcare issue warranting hospitalization) may be obtained by direct contact with [name], the study PI. If it is determined a patient cannot have a 6 month (5-7 ½ month) MRI, the patient will continue on study as per protocol.

The 24 – 27 month MRI should be obtained within 30 days prior to the last dose of study medication. For time periods outside of these ranges, special permission for extenuating circumstances (e.g., significant healthcare issue warranting hospitalization) may be obtained by direct contact with [name], the study PI.

Due to unknown risks and potential harm to the unborn fetus and because some methods of birth control are not 100% reliable, it is suggested that women of childbearing potential take a pregnancy test prior to each MRI exam, as written in the informed consent form. It is also suggested that a

negative serum or urine pregnancy test be performed within 10 days of each MRI exam. Each site should follow their institution's policies.

MRI may be performed without contrast but it is preferred contrast be used to better define the cardiac structures. If the site has a signed contract with Bracco and ProHance is supplied, the site will be responsible for maintaining a careful record of the inventory and disposition of the ProHance® received.

Neurocognitive Function

Cognition and Quality of Life

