7.9 Off-Study Criteria

Participants may go 'off-study' for the following reasons: the protocol intervention and any protocol-required follow-up period is completed, adverse event/serious adverse event, lost to follow-up, concomitant medication, medical contraindication, withdraw consent, or death.

Since the study inception and development of the inclusion/exclusion criteria, guidelines regarding the potential administration of statins have been released by the ACC/AHA on November 12, 2013. These new guidelines suggest the use of a calculator to assess cardiovascular risk with subsequent initiation of statin therapy based on that risk. Concomitant with the release of the guidelines, however, have been several articles suggesting that the calibration of the calculator was somewhat imperfect, particularly in regards to data from both the Nurses' Health and Physicians' Health studies.

As a result of these controversies, the study investigators elected to leave the initial entry and exclusion criteria intact. Importantly however, their respective primary care physician will be mailed a letter raising their awareness to the publication of these guidelines. If the study participant and their primary care physician elect to initiate statin therapy, they will be counseled to stop their study drug and notify the respective investigators at their study site. They will still be allowed to participate in all other aspects of the trial as an open label statin user. Data analyses regarding intention to treat as well as treatment effect will be performed.

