12.3. Analysis Plan

The primary hypothesis for Specific Aim 1 is that statin use will protect against a harmful reduction in LVEF measured over 24 – 27 months for patients with breast cancer or lymphoma who receive Anthracycline-based therapy. All randomized patients will be used in the analysis to compare groups (“intent to treat” approach). Since LVEF is measured on a continuous scale and this is a randomized trial, our primary analysis will fit an analysis of covariance (ANCOVA) model that compares the 24- 27 month values of LVEF between groups adjusting for the baseline (pre-treatment) levels of LVEF and stratification factors. Note that patients are stratified by planned dose and that is the stratification that will be used in the analysis, even if the patient ends up getting a different dose. This analysis will address the first specific aim.

To address the second primary aim, we will examine whether the early treatment effect of statin use (6 months post randomization) predicts the long-term (24 – 27 month) effect of statins. Pilot data (Section 2) suggest that Anthracycline-based therapy injury occurs early and concomitant statin use attenuates this early Anthracycline-based therapy-mediated injury. We will fit an ANCOVA model that compares the 24- 27 month LVEF values for the treated and control groups and will also include covariates for the baseline LVEF and 6-month change in LVEF values. We will examine the treatment by 6-month LVEF change interaction to determine whether the correlation between early and late changes in LVEF differs by treatment. Thus, this model will have 4 terms of interest: the main effect for treatment, the main effect for the change in LVEF after 6 months, the main effect for baseline pre-treatment LVEF, and the treatment by change in LVEF after 6-month interaction. If the interaction is non-significant, we will examine the model with the 3 main effects. Since there may be limited power to test this interaction, we will use a 0.15 threshold for testing significance of the

interaction term in the model.

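### The final MRI window is tied to the last dose of study drug, which conflicts with the 24–27 month scan planned for every randomized patient, including those who stop drug early

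*Combined protocol and SAP*

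**What the plan says.** The last-dose rule appears in three places.

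- Section 7.2: the 24–27 "month MRI should be obtained within 30 days prior to the last dose of study medication".
- The bold note above the Section 7.7 table: "24 month MRI should be obtained within 30 days prior to the last dose of study medication".
- Footnote A3 to that table, attached to the MRI cell in the 24–27 month column: "MRI should be obtained within 30 days prior to the last dose of study medication".

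Section 7.2 and footnote A3 allow scans at other times only with the study PI's permission in exceptional situations; the example is a health problem needing hospitalization. The table's general allowance of plus or minus 30 days applies only where nothing else is specified, so the MRI rule displaces it.

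Other sections keep patients in the trial after they stop study drug. Section 5.6.1, on recurrent myalgia or raised labs: "Patient will be considered off study medication but will continue to be followed". Section 7.9, on patients who start a statin with their own physician: "They will still be allowed to participate in all other aspects of the trial as an open label statin user". Section 7.8 continues follow-up, where possible, to collect endpoint data on the schedule of events. Section 7.4 gives all participants a cardiac MRI between 24 and 27 months.

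On analysis, Section 12.3 states: "All randomized patients will be used in the analysis to compare groups". Section 5.7.1 says the same and adds that adherence does not matter for inclusion. Section 3.1.1, the COVID-19 amendment, describes the aim differently: "we will evaluate the efficacy of the study drug on patients who take the drug until their final outcome assessments".

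**The concern.** Aim 1 asks about LVEF at 24 months in everyone randomized. A window that closes on the day of the last dose suits only patients who take drug to the end. In an unplanned stop, the window has usually closed before the site knows which dose was the last. The site can then scan at about the time of stopping, which is not a 24-month measurement; seek a discretionary exception for month 24; or not scan.

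Each choice depends on something that happened after randomization. Some reasons for stopping, such as myalgia and raised liver enzymes, are listed in Section 6.2 as effects of atorvastatin, so stopping may differ between arms. At stake is whether the primary comparison remains one of all randomized patients.

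**Working it through.** **Do the window and the label fit together?** Take 30 days as one month.

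| Last dose of study drug | Window under the last-dose rule | Fit with 24–27 months |
|---|---|---|
| Month 8 (example of an early stop) | Months 7–8 | None; the label opens 16 months later |
| Month 24 | Months 23–24 | They meet at one edge |
| Month 27 | Months 26–27 | Inside |

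The rule works for patients still on drug at the end. It fails for early stoppers, including open-label statin users, who are counselled to stop study drug.

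**Does other text resolve it?** Section 7.4 establishes that the visit exists for everyone. Section 7.8 sends the site to the schedule of events, but the MRI cell there carries footnote A3, so following 7.8 leads back to the last-dose rule. Footnote J covers open-label patients for diaries; A3 has no such provision. Footnote A2 times the 6-month scan by calendar (5 to 7½ months), so the protocol already has a form of words that works off drug.

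**Does the primary model absorb mistiming?** The ANCOVA in Section 12.3 adjusts for baseline LVEF and strata. It has no term for scan date, although 3.1.1 says exact timing can be accounted for.

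**The plan's own figure.** Inputs from Section 12.6: SD 7.7, r = 0.5, n = 100 per group, two-sided alpha 0.05, 80% power.

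Detectable difference = 7.7 × √(2 × (1 − 0.25)) × (1.96 + 0.84) / √100 = 2.64 points, as in Table 5. Enrolment: 200 / (1 − 0.28) = 278, as stated. Neither figure is in question.

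**Illustration of the gap.** The documents give neither a stopping rate nor the share of stoppers scanned. Assume that a share q stops early, that the on-drug effect is 2.64, that stoppers keep a fraction k of it, and that stoppers are otherwise like the rest.

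- All-randomized effect = 2.64 × (1 − q(1 − k)).
- Gap if no stopper is scanned = 2.64 × q × (1 − k).

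| q | k = 0 | k = 0.5 | k = 1 |
|---|---|---|---|
| 10% | 0.26 | 0.13 | 0 |
| 20% | 0.53 | 0.26 | 0 |
| 30% | 0.79 | 0.40 | 0 |

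**Illustration of lost precision.** If the unscanned stoppers come on top of the planned 28% loss, n per group = 100 × (1 − q), with adjusted SD 7.7 × √0.75 = 6.67. Power for 2.64 points falls from 79.9% to 75.7% (90 per group), 70.7% (80) or 64.9% (70) at q = 10%, 20% or 30%.

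**The case against.** The strongest reply is that the plan already answers the question. Footnote A3 itself calls the scan the 24–27 month MRI; Section 7.4 requires it for all participants; 7.8 asks for endpoint data after stopping; 5.7.1 and 12.3 fix the analysis set. On that reading, the last-dose clause merely tells sites to scan completers before drug runs out. The wording is advisory, and hospitalization is only an example of grounds for an exception. Section 12.4 also plans methods for informative missing data.

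Much of this stands. A reader might infer that early stoppers have no valid 24-month scan, or that the primary result will describe on-drug patients only. The documents support neither: the visit exists for everyone, and drift requires sites to skip or move scans. Section 3.1.1 explains extra drug supply during the pandemic and does not define an analysis population.

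A reader might also take the 28% loss as a stopping rate and conclude that the effect would be overstated by 1/0.72 − 1 = 39%. That fails too: 28% is loss to follow-up, the sum assumes that no stopper is scanned and no benefit persists, and the protocol's premise of early injury makes some persistence plausible.

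Nor does the capsule count show bias. Shipments 1 and 2 hold 4 × 180 = 720 capsules against about 730 days, a difference of about 10 days, and a third shipment is available if needed.

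What the reply does not remove is the conflict. A site applying the specific rule finds a month-24 scan in an early stopper out of window unless the PI agrees. The check in 12.4 compares baseline characteristics, whereas stopping drug occurs after randomization.

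**Conclusion.** The concern holds as a conflict between passages about the primary-endpoint scan. The last-dose window in Sections 7.2 and 7.7 cannot be applied to early stoppers together with the 24–27 month label, Section 7.4, Section 7.8 and the all-randomized analysis. Selection on adherence is a risk if sites follow the rule literally; it is not an established consequence of the plan.

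The size cannot be computed from the documents. The illustrative 0 to 0.79 points on 2.64 rests on assumed stopping of 10–30%, no stopper scanned, and persistence of benefit between full and none. It is not a bound: unequal stopping between arms, or placebo patients who take open-label statin, would change it. The planned figures of 2.64 points and 278 patients are unaffected.

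The point deserves correction before analysis because it concerns the primary endpoint. It is about the timing of assessment only; no view is taken on when drug should be stopped.

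**What to change.** - In Section 7.2, the note above the 7.7 table and footnote A3, define the final MRI window as 24–27 months from a stated origin (randomization or first dose) for every randomized patient, whether on study drug, off it or on open-label statin. An origin is needed because Section 1 counts from the start of chemotherapy, 12.2 from its receipt and 3.1.1 from the start of the study.
- Keep the timing before the last dose only as a preference for patients still taking study drug.
- Do not require special permission merely because drug has stopped.
- Reword the 3.1.1 sentence so that it agrees with Section 12.3.

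The cost is wording. No visit or procedure is added, since Sections 7.4 and 7.8 already ask for these scans. The change cannot recover patients who leave follow-up by other routes, such as those unblinded under Section 6.9.

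The downside is that some final scans will be off drug, so the estimate may be less favourable. At the unfavourable end (k = 0, 100 per group scanned), the all-randomized effect would be 2.38 points at 10% stopping, with 71% power, or 1.85 points at 30%, with 50% power. That reflects the question the plan says it is asking.
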